4.2. Exclusion Criteria

Subjects who meet any of the following exclusion criteria are not eligible to participate in the study:

1. If a Gram stain from a respiratory sample is available and sample shows only Gram-positive cocci.
2. Subjects who have known or suspected community-acquired bacterial pneumonia, atypical pneumonia, viral pneumonia including COVID-19, or chemical pneumonia (including aspiration of gastric contents, inhalation injury).
3. Subject who has HABP/VABP caused by an obstructive process, including lung cancer (or other malignancy metastatic to the lungs resulting in pulmonary obstruction) or other known obstruction.
4. Have received effective systemic and inhaled Gram-negative antibacterial drug therapy for the index infection of HABP/VABP for a continuous duration of more than 24 hours during the previous 72 hours prior to randomization.
[REDACTED]
5. Has a concurrent condition or infection that, in the investigator's judgment, would preclude evaluation of therapeutic response (e.g., active tuberculosis, cystic fibrosis, granulomatous disease, a disseminated fungal infection, invasive fungal pulmonary infection, or endocarditis).
6. Subjects who have central nervous system infection (e.g., meningitis, brain abscess, shunt infection).
7. Documented presence of immunodeficiency or an immunocompromised condition including hematologic malignancy, bone marrow transplant, known history of human immunodeficiency virus infection with a CD4 count $<200/\text{mm}^3$, or requiring frequent or prolonged use of systemic corticosteroids (≥ 20 mg of prednisone/day or equivalent for >4 weeks) or other immunosuppressive drugs (e.g., for organ transplantation or autoimmune conditions).
8. Documented hypersensitivity to any carbapenem antibacterial agent or documented severe hypersensitivity to any other type of beta-lactam antibacterial agent, or previous severe adverse drug reaction to any β -lactam antibiotics, or any of the excipients used in the study drug formulations.
9. History of a seizure disorder (requiring ongoing treatment with anti-convulsive therapy or prior treatment with anti-convulsive therapy within the last 3 years).
10. Renal function at screening as estimated eGFR <15 mL/min or >250 mL/min, calculated as individual eGFR derived from Modification of Diet in Renal Disease formula.

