7.5.2. Chest Imaging

Chest imaging (Chest x-ray or computed tomography scan) will be performed at screening and is required for diagnosis and assessment of eligibility. [REDACTED]

[REDACTED] The investigator's (or qualified designee's at the site) interpretation of the chest imaging may be used to make the enrollment decision if a radiologist's interpretation is not available.

Local reading of screening chest imaging by a radiologist is required for all subjects including subjects enrolled based on the interpretation of the investigator. The local radiologist's interpretation will be captured.

Details on the interpretation from both the investigator (if used for enrollment) and the radiologist report will be collected including the presence and location of pneumonia findings such as infiltrates, opacities, and consolidation for all screening films. In addition, any radiology reports will be collected if relevant to an SAE as well as follow-up reports if results are clinically significant.

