3.2.8. Clinically Evaluable (CE) Population

All subjects from the MITT who receive at least 72 hours of IV study treatment, have an appropriate diagnosis of HABP/VABP, have no important protocol deviations that would affect the assessment of clinical outcome, and have no missing nor indeterminate assessment of clinical outcome.

Based on the above definition, subjects who meet all of the following criteria will be included in the CE population:

- Duration of exposure to study drug ≥ 72 hours .
- Meets Inclusion Criterion 4: Has HABP or VABP, as defined below, requiring intravenous antimicrobial therapy. Note: HABP is defined as symptoms of acute bacterial pneumonia occurring at least 48 hours after hospitalization or within 7 days of discharge from an acute or chronic care facility (e.g., long term care, rehabilitation center, hospital or skilled nursing home). Subjects may have developed acute respiratory failure requiring mechanical ventilation for HABP (vHABP). VABP is defined as acute bacterial pneumonia for which the subject has received mechanical ventilation via endotracheal (or transnasal tracheal) intubation or tracheotomy for ≥ 48 hours.
- Subjects who do not meet Exclusion Criterion 2: Subjects with known or suspected community-acquired bacterial pneumonia, atypical pneumonia, viral pneumonia including novel coronavirus pneumonia (COVID-19), or chemical pneumonia (including

aspiration of gastric contents, inhalation injuries).

- No sustained discontinuation of the test drug \geq for 48 hours (if discontinued and total number of discontinuations < 8).
- No co-prohibition of systemic gram-negative antibiotics for \geq 72 hours (screened based on concomitant medication and co-prohibition regimen deviation data).
- No EOT or TOC Clinical Assessments Uncertain/Missing (Clinical Assessments at EOT and TOC visits may not be Uncertain or Missing. Note: Death resulting in a clinical assessment not being collected is not considered missing).

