3.2.9. Microbiologically Evaluable (ME) Population

All subjects in micro-MITT who received at least 72 hours of intravenous study treatment, had an appropriate diagnosis of HABP/VABP, had no significant protocol deviations that could affect the microbiologic efficacy evaluation, and had no microbiologic efficacy evaluations that were missing or inconclusive.

Based on the above definition, subjects who meet all of the following criteria will be included in the ME population:

- Eligible for micro-MITT population.
- Duration of exposure to the study drug \geq 72 hours.
- Meets Inclusion Criterion 4: Has HABP or VABP, as defined below, requiring intravenous antimicrobial therapy. Note: HABP is defined as symptoms of acute bacterial pneumonia occurring at least 48 hours after hospitalization or within 7 days of discharge from an acute or chronic care facility (e.g., long term care, rehabilitation center, hospital or skilled nursing home). Subjects may have developed acute respiratory failure requiring mechanical ventilation for HABP (vHABP). VABP is defined as acute bacterial pneumonia in subjects receiving mechanical ventilation via endotracheal (or transnasal tracheal) intubation or tracheotomy for ≥ 48 hours.
- Subjects who do not meet Exclusion Criterion 2: Subjects with known or suspected community-acquired bacterial pneumonia, atypical pneumonia, viral pneumonia including novel coronavirus pneumonia (COVID-19), or chemical pneumonia (including aspiration of gastric contents, inhalation injuries).
- No sustained discontinuation of the test drug \geq for 48 hours (if discontinued and total number of discontinuations < 8).
- No co-prohibition of systemic gram-negative antibiotics for \geq 72 hours (screened based on concomitant medication and co-prohibition regimen deviation data).
- No EOT or TOC microbiologic evaluations are indeterminate/missing (Evaluation of microbial efficacy at EOT and TOC visits may not be indeterminate/missing. (Note:

Lower respiratory tract samples are not collected at the EOT/TOC/LFU visit, and microbial efficacy is assessed on the basis of clinical efficacy results and is not missing).

- Only pathogenic bacteria identified in lower respiratory tract samples were considered.

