4.2. Protocol Deviations

Subjects who did not meet the eligibility criteria for study entry but enrolled in the study, will be summarized regardless of whether they were exempted by the sponsor or not. The summary will present the number and percentage of subjects who did not meet at least 1 eligibility criterion and the number of subjects who did not meet specific criteria by treatment group based on the ITT population. A by-subject listing will be provided for those subjects who did not meet at least 1 eligibility (inclusion or exclusion) criterion.

Protocol deviations occurring after subjects entered the study are documented during routine monitoring. The number and percentage of subjects with important protocol deviations by deviation reason (e.g., nonadherence to study drug, violation of select inclusion/exclusion criteria) will be summarized by treatment group for the ITT population. A by-subject listing will be provided for those subjects with important protocol deviation.

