5.2. Other Baseline Characteristics Analysis

Other baseline characteristics include:

- Country/region (China and the rest of the world)
- Type of infection at baseline (non-ventilated HABP, mechanically ventilated HABP, VABP)
- APACHE II score (continuous variable)
- APACHE II scores (<10, 10 to <15 and \geq 15)
- Sequential Organ Failure Assessment (SOFA) score
- Glasgow Coma Scale (GCS) score (continuous variable)
- Glasgow Coma Scale (GCS) score (<7 and \geq 7)
- Baseline ICU admission (yes/no/missing), i.e., ICU admission at the time of the first dose; if the ICU admission time is missing, the admission time is filled in using 00:00, and the ICU departure time is filled in using 23:59
- Baseline eGFR (continuous variable)
- Baseline eGFR (<30 mL/min, 30 to <60 mL/min, 60 to <90 mL/min, 90 to <150 mL/min, 150 to < 250 mL/min and \geq 250 mL/min)
- Baseline Liver Function (Normal, Abnormal), Abnormal liver function was defined as subjects with baseline results of any of the ALT, AST, ALP and total bilirubin in laboratory tests that were outside the normal range of values.
- Received antimicrobial therapy for this HABP/VABP (yes/no)
- Whether the subject received systemic or inhaled effective gram-negative antimicrobial medication for more than 24 hours sustained against a specific infection of HABP/VABP within 72 hours prior to randomization (Yes/No)
 - Whether the subject's previous antibiotic treatment was considered a clinical failure (yes/no), only if the answer to the above question was "yes".

- Whether the subject required mechanical ventilation because of treatment failure (yes/no), only if the answer to the above question was "yes".
- Baseline lower respiratory tract gram-negative infections (no; yes: mono/poly)
- Top 5 ranking of respiratory pathogens in the lower respiratory tract at baseline HABP/VABP (5 most frequent in total groups)
- Resistance to gram-negative pathogenic bacteria of the respiratory tract at baseline (carbapenem-resistant/non-resistant)
- Concomitant bacteremia at baseline (yes/no)

These baseline characteristics will be summarized by test drug group, control drug group, and aggregate, using descriptive statistics for continuous variables and number and percentage of subjects for categorical variables. These baseline characteristics will be summarized based on the safety population and the micro-MITT population.

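### The operational CE and ME lists omit exclusion criterion 4 and inclusion criterion 7, so subjects enrolled in violation of either one stay in these secondary analysis sets

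*SAP*

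**What the plan says.** SAP 3.2.8 repeats the protocol's general CE definition (Protocol 8.2): at least 72 hours of IV study treatment, an appropriate diagnosis of HABP/VABP, a usable clinical assessment, and a requirement to "have no important protocol deviations that would affect the assessment of clinical outcome". It then gives the working rule: "Based on the above definition, subjects who meet all of the following criteria will be included in the CE population". SAP 3.2.9 does the same for ME: "Based on the above definition, subjects who meet all of the following criteria will be included in the ME population".

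The diagnosis part of both lists begins "Meets Inclusion Criterion 4: Has HABP or VABP, as defined below, requiring intravenous antimicrobial therapy" and adds that exclusion 2 (community-acquired, atypical, viral or chemical pneumonia) must not apply. No other eligibility criterion is named.

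Other relevant provisions:

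- **Prior therapy.** Protocol 4.2, exclusion 4, reads in part "Have received effective systemic and inhaled Gram-negative antibacterial drug therapy for the index infection of HABP/VABP", with a limit of 24 continuous hours in the 72 hours before randomization. The text that follows is blacked out. SAP 5.2 records a related baseline item: "Whether the subject received systemic or inhaled effective gram-negative antimicrobial medication for more than 24 hours". Two follow-up items concern failure of the earlier treatment.
- **Infiltrate.** Protocol 4.1, inclusion 7, requires a new or progressive infiltrate on chest imaging. Protocol 7.5.2 lets the investigator's reading support enrollment when no radiologist's reading is available, but also states: "Local reading of screening chest imaging by a radiologist is required for all subjects". SAP 8.4.1 plans only a listing of imaging.
- **Ineligible subjects.** SAP 4.2: "Subjects who did not meet the eligibility criteria for study entry but enrolled in the study, will be summarized".

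**The concern.** CE and ME are meant to show the treatment effect in correctly diagnosed, protocol-compliant subjects. A program that follows the bullets would keep a subject whose infection had already been treated effectively beyond the permitted time, or whose imaging did not show the required infiltrate. The general definition would give good reason to remove both. The definition and the algorithm can thus yield different sets, and the algorithm states who is included.

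If such subjects do about equally well or badly whichever study drug they receive, they dilute a real difference. In a non-inferiority trial that favors the test drug. At stake are secondary results: mortality and clinical success in CE and ME, and microbiological and overall success in ME (SAP 8.2), which are analyzed in a manner similar to the primary endpoint.

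**Working it through.** **1. The plan's own figure.** The design calculation in SAP 1.3 concerns the primary endpoint: 10% mortality in each arm, 10-point margin, one-sided 0.025, 300 and 150 subjects (SAP 1.2).

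SE = √(0.1×0.9/300 + 0.1×0.9/150) = √0.0009 = 0.030. Power = Φ(0.10/0.030 − 1.96) = Φ(1.373) = 91.5%.

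The stated power of more than 90% reproduces. It is not in dispute, and the CE and ME lists do not touch it.

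**2. The CE list against the two criteria.**

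| CE bullet (SAP 3.2.8) | Catches an exclusion 4 violation? | Catches an inclusion 7 violation? |
|---|---|---|
| Exposure of at least 72 h | No | No |
| Inclusion 4 met (timing, ventilation, need for IV therapy) | No | No; imaging is not part of it |
| Exclusion 2 not met | No | Only if another listed type of pneumonia is known or suspected |
| No dosing gap of 48 h or more | No | No |
| No prohibited systemic Gram-negative antibiotic for 72 h or more | Not if stopped before the first dose | No |
| EOT and TOC assessments available | No | No |

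The antibiotic bullet is screened on concomitant medication and related deviations. SAP 7.1 leaves any drug stopped before the first study dose out of the concomitant medication summary, so earlier therapy that ended by then is not seen there.

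The ME list adds micro-MITT membership and uses microbiological assessments. That requires a baseline lower-respiratory Gram-negative pathogen susceptible to both drugs (SAP 3.2.4), which gives partial protection. The protection is incomplete for two reasons. The culture may come from up to 48 hours before randomization (SAP 3.7.3). And where no later culture exists, clinical success becomes presumed eradication (SAP 8.2.3), which SAP 3.2.9 does not treat as missing.

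**3. Possible size, on assumed values.** The documents give no CE or ME size, no success rate and no number of affected subjects. Let *f* be the fraction of the set with the same success rate *s* in both arms. Let control success among the rest be *p* and the true difference −10 points. Then:

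- control: c = (1−f)p + f·s
- test: t = (1−f)(p−0.10) + f·s
- observed difference: t − c = −0.10(1−f)
- chance that the lower 95% limit clears an assumed −10-point margin: Φ((0.10 + t − c)/SE − 1.96), with SE = √(c(1−c)/n_c + t(1−t)/n_t)

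Example with n_t = 300, n_c = 150, p = s = 0.70, f = 0.10: c = 0.70, t = 0.61, SE = √(0.70×0.30/150 + 0.61×0.39/300) = 0.0468. The chance is Φ(0.01/0.0468 − 1.96) = 4.0%.

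The ranges below cover CE sizes of 300 to 450 at 2:1, p of 60% to 70%, and s from p up to 90%.

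| f | Observed difference (points) | Chance of wrongly concluding non-inferiority |
|---|---|---|
| 0 | −10.0 | 2.5% |
| 5% | −9.5 | 3.0–3.2% |
| 10% | −9.0 | 3.6–4.1% |
| 20% | −8.0 | 5.2–6.5% |
| 30% | −7.0 | 7.2–10.1% |

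**The case against.** The strongest reply is that the lists derive from the general definition, which already asks for a proper diagnosis and no important deviation. SAP 4.2 gives violation of selected eligibility criteria as an example of an important deviation. Protocol Appendix 5 says deviations that invalidate the data lead to exclusion. SAP 3.2 settles populations before unblinding. All true, and it means the fault is incomplete wording rather than a wrong concept. But none of these provisions names exclusion 4, inclusion 7, CE or ME in a way that overrides a list stating who is included.

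It can also be said that prior therapy is examined elsewhere: baseline tables (SAP 5.2), eligibility failures by criterion (SAP 4.2), and subgroups by prior therapy and its failure (SAP 8.1.2.4, 8.2.2.2). Those outcome subgroups are in MITT. They inform the reader but do not change who is in CE or ME.

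Three further objections stand and limit the point:

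- A reader might infer that CE should require a radiologist-confirmed infiltrate. The protocol does not make that an entry condition, and a subject enrolled on the investigator's permitted reading is compliant.
- A reader might infer that everyone with more than 24 hours of prior therapy is wrongly kept. Part of exclusion 4 is blacked out, and the follow-up items in SAP 5.2 suggest that exceptions may exist. Some of these subjects may be eligible.
- A reader might infer that the sets are filled with subjects already cured or without pneumonia. Entry requires active signs (inclusion 5 and 6), the investigator must judge 7 to 14 days of IV treatment necessary (Protocol 3.1), CE requires 72 hours of study drug, and ME a baseline pathogen. Waivers are not permitted (Protocol 4), and SAP 4.2 is a reporting rule that says nothing about frequency.

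**Conclusion.** The point holds as a gap between definition and algorithm. Followed as written, SAP 3.2.8 and 3.2.9 retain subjects who violate exclusion 4 or inclusion 7 and pass the other bullets. The likely direction is toward no difference, mainly in CE and less in ME.

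The size is unknown. The illustration rests on four assumptions: a true 10-point deficit, an invented fraction *f*, equal outcomes in both arms for that fraction, and a 10-point margin that the plan states for mortality and not visibly for clinical success. At 5% the shift is half a point; it becomes material only if such enrollment was common. The documents do not support a claim that CE or ME results are biased by any particular amount, nor any doubt about the primary MITT mortality analysis on this ground.

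Separately, Protocol exclusion 4 joins the systemic and inhaled routes with *and*, while the SAP 5.2 item joins them with *or*. Read literally, these describe different subjects. The protocol phrase can also be read as simply naming both routes, and the blacked-out text may settle it. The two must be reconciled so that a check against exclusion 4 has one meaning.

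**What to change.** Before unblinding:

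1. Add two bullets to both SAP 3.2.8 and 3.2.9: the subject does not violate exclusion 4 as fully worded in the protocol, including any exceptions; and the subject meets inclusion 7.
2. Report, per arm, how many subjects each new rule removes from CE and from ME. This replaces the assumed *f* with a count.
3. Use the captured local radiologist's reading only for a sensitivity analysis or for a count of discordance with the investigator's reading. Do not make it a condition for CE or ME.
4. Reconcile the description of prior therapy in Protocol exclusion 4 (synopsis and 4.2) with the item in SAP 5.2.

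The cost is SAP wording and some programming on data already collected. CE and ME become slightly smaller; MITT does not change. If the SAP is already final, SAP 1 requires the change to be documented in the clinical study report.

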1. SUMMARY

This Statistical Analysis Plan (SAP) describes the study XNW4107-302 (A Multicenter, Randomized, Double-Blind, Comparative, Phase 3 Study to Evaluate the Efficacy and Safety of Intravenous Imipenem/Cilastatin-XNW4107 in Comparison with Imipenem/Cilastatin/Relebactam in Adults with Hospital-Acquired Bacterial Pneumonia or Ventilator-Associated Bacterial Pneumonia) Clinical Study Report (CSR) statistical analysis methods and data used in Tables, Figures, and Lists (TFL). This SAP is based on the Clinical Study Protocol (V4.1) dated April 23, 2024 and the electronic Case Report Form (eCRF) version 8.0. The SAP will be finalized before the database is finally locked. Any changes made after the SAP is finalized will be documented in the CSR.

For the purposes of this SAP, test drug will be defined as Imipenem/Cilastatin-XNW4107 (IMI-XNW4107), control drug will be defined as Imipenem/Cilastatin/Relebactam (IMI/REL), and investigational drug will include both test and control drugs.

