3.2. Analysis Population

The analysis population defines the subjects included in the analysis. This section contains all analytic populations and their definitions. The subjects included in each population will be determined prior to the unblinding analysis. All tables, figures, and lists will be subtitled with the corresponding analysis population.

For each population, the number and percentage of subjects eligible for inclusion will be summarized by treatment group, as well as the number and percentage of subjects excluded and their primary reason for exclusion.

Subjects who are randomized will be defined as subjects who have filled out the randomization information on the CRF D1 visit randomization page.

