6.1. Duration of Exposure to Study Drug

Total duration of exposure to study drug will be defined as following and will be expressed in days.

Duration of exposure to study drug = (last dose time - first dose time)/24 hour.

The total duration of exposure to study drug will be summarized using descriptive statistics and using the number and percentage of subjects exposed through the following time periods: 1 day, 2 days,, 14 days. Summaries will be provided by treatment group for the Safety Population

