6.2.1. On-Treatment Adherence

The level of treatment period adherence to an investigational drug dosing regimen depends on the percentage of the total amount of investigational drug received by the subject relative to the total amount of investigational drug expected to be used under the investigational drug regimen during the subject's actual treatment period.

The total number of infusions of study drug and the total number of infusions of study drug expected to be used during the subject's actual treatment according to the study drug regimen will take into account the data in the EDC.

The level of adherence during the treatment period is expressed as a percentage and is calculated according to the following formula:

$$\text{On-Treatment Adherence (\%)} = \frac{\text{Total Number of Study Drug Doses Administered}}{\text{The total number of infusions of the study drug expected to be used according to the study drug regimen during the subject's actual treatment}} \times 100$$

Descriptive statistics for the level of on-treatment adherence with the number and percentage of subjects belonging to adherence categories (< 80%, ≥ 80 to $< 90\%$, $\geq 90\%$) will be provided by treatment group for the Safety Population.

A by-subject listing of study drug administration will be provided by subject ID number (in ascending order) and visit (in chronological order).

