8.2. Secondary Efficacy Endpoint

The secondary endpoints for this study are the following:

- Day 28 all-cause mortality rate in the MITT population
- Day 14 and Day 28 all-cause mortality rate in the micro-MITT, extended micro-MITT, CE, ME, and CR-MITT populations
- The proportion of subjects with clinical success as evaluated by the investigator at Day 4, EOT, TOC, and LFU visits in the MITT, micro-MITT, extended micro-MITT, CE, ME, and CR-MITT populations
- The proportion of subjects with microbiological success at EOT, TOC, and LFU visits in the micro-MITT, extended micro-MITT, CR-MITT, and ME populations
- The proportional of subjects with microbiological success by pathogen at EOT, TOC, and LFU visits in the micro-MITT, extended micro-MITT, ME, and CR-MITT populations.
- The proportion of subjects with overall success at EOT, TOC, and LFU visits in the micro-MITT, extended micro-MITT, ME, and CR-MITT populations.

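### As worded, the interruption criterion for the CE and ME populations applies only to the IMI-XNW4107 arm; it should name both arms

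*SAP*

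**What the plan says.** SAP section 1 fixes the vocabulary. It states that "test drug will be defined as Imipenem/Cilastatin-XNW4107 (IMI-XNW4107"), gives IMI/REL as the control drug, and adds that "investigational drug will include both test and control drugs".

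SAP 3.2.8 (CE) and 3.2.9 (ME) each open with a definition that does not distinguish the arms, followed by a list of criteria. A subject who meets every item on the list is included. One item, worded the same in both lists, is "No sustained discontinuation of the test drug" for 48 hours or more, with a parenthetical limit of fewer than 8 discontinuations. Neither list has a matching item for the control drug. The 72-hour exposure item in the same lists uses *study drug* instead.

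Three other places matter:

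- SAP 3.2: "The subjects included in each population will be determined prior to the unblinding analysis".
- SAP 6.1: "Duration of exposure to study drug = (last dose time - first dose time)/24 hour".
- SAP 6.2.1: adherence summaries "will be provided by treatment group for the Safety Population".

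CE and ME are used for listed secondary endpoints. SAP 8.2 includes "Day 14 and Day 28 all-cause mortality rate in the micro-MITT, extended micro-MITT, CE, ME, and CR-MITT populations", clinical success in both sets, and microbiological and overall success in ME.

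**The concern.** An exclusion for interrupted dosing depends on something that happens after randomisation. Applied to both arms, it gives the usual evaluable-population analysis with its known limits. Applied to one arm, it removes subjects from IMI-XNW4107 and keeps their counterparts on IMI/REL, so the two groups are no longer selected in the same way.

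For clinical and microbiological success, this would favour IMI-XNW4107 if interrupted subjects do worse. For mortality the direction is unclear: a subject who resumes after a gap has by definition survived it, so removing such subjects could raise or lower the observed rate.

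A programmer who follows the SAP's own definitions would build the one-arm version. The primary Day 14 mortality comparison in MITT does not use this criterion and is not at stake.

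**Working it through.** **1. What the term means across the SAP.** Section 1 defines *test drug* as one arm. The other uses agree:

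- 3.2.4 and 3.2.6 name the test and control drugs separately when both are meant.
- 3.6.2 ties the term to IMI-XNW4107 when setting the provisional breakpoint.
- 5.2 has characteristics "summarized by test drug group, control drug group, and aggregate".
- 8.1.2.2 contrasts test with control drug as the treatment covariate.

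None of these uses the term for both arms.

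**2. Whether the limit itself is specific to one arm.** Both arms are dosed every 6 hours (Protocol 5.8; SAP 1.2). 48 h / 6 h = 8 doses, which matches the limit of fewer than 8. It carries over unchanged to IMI/REL.

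**3. Whether another listed criterion catches a control-arm gap.** The 72-hour item is the only candidate. By the SAP 6.1 formula, exposure is last dose minus first dose, so time off drug in between still counts. Example:

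- Scheduled doses from hour 0 to hour 72: 72/6 + 1 = 13.
- Doses given at hours 0, 6, 12, 66 and 72: 5.
- Doses missed: 13 − 5 = 8.
- Longest gap between doses: 66 − 12 = 54 h. Counted from the first missed dose at hour 18, it is 66 − 18 = 48 h.
- Exposure: 72 − 0 = 72 h = 3.0 days, so the 72-hour item is met.
- Adherence: 5/13 = 38%. Adherence is summarised but is not a condition for CE or ME.

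With the other criteria met, this subject leaves CE if on IMI-XNW4107 and stays if on IMI/REL.

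**4. Illustrative size.** The documents give no interruption rate and no outcomes for interrupted subjects, so *g*, *d* and *m* below are assumptions.

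*Success.* Removing a fraction *g* whose success is lower by *d* than the rest raises the arm's rate by *g* × *d*:

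- *g* = 2%, *d* = 10 points: 0.02 × 0.10 = 0.2 points.
- *g* = 8%, *d* = 30 points: 0.08 × 0.30 = 2.4 points.

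*Mortality.* With the planned rate of 10% (SAP 1.3) and mortality *m* in interrupted subjects, the change is (0.10 − *g m*)/(1 − *g*) − 0.10:

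| *g* | *m* = 0% | *m* = 20% |
|---|---|---|
| 2% | 0.100/0.98 − 0.10 = +0.20 points | 0.096/0.98 − 0.10 = −0.20 points |
| 8% | 0.100/0.92 − 0.10 = +0.87 points | 0.084/0.92 − 0.10 = −0.87 points |

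Applying the criterion to both arms removes the asymmetry.

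**The case against.** The best reply is that a one-arm rule could not be carried out under the plan's own process. Populations are fixed before unblinding, and Protocol Table 4 limits the unblinded statistician and programmers to supporting DMC reviews and safety surveillance. Blinded staff could apply the item only to everyone. The SAP's drug terms are also loose: *study drug* is not among the terms defined in section 1, 3.2.10 uses it apparently for the test arm, and the bullet reads like a rough translation. This is good evidence that both arms were intended. It does not correct the text: the blinding rule conflicts with the literal criterion without replacing it, and 3.2.10 shows that the SAP does set one population by arm.

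A second reply is that the opening definitions exclude important protocol deviations affecting the outcome assessment, that SAP 4.2 gives nonadherence as an example of a deviation reason, and that Protocol Appendix 5 has deviations classified before the final analysis. A control subject with 38% adherence might be removed that way. But none of these places assigns a control-arm interruption to exclusion from CE or ME, and the lists are the stated implementation of the definitions.

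Two further points stand. The magnitudes are assumption-driven: with a 40-point success deficit and a 10% interruption rate, the shift would be 0.10 × 0.40 = 4.0 points. And the parenthetical limit is unclear on whether the 8 are consecutive or cumulative and how it combines with the 48-hour condition; changing the drug term does not resolve that.

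**Conclusion.** The criterion is wrong as written. Under the SAP's definitions it excludes interrupted subjects from IMI-XNW4107 only, in two populations that support listed secondary endpoints, and no other listed criterion restores symmetry. A both-arm rule was probably intended; if it is programmed that way, there is no differential exclusion and only the wording needs correcting.

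If it is programmed literally, the CE and ME comparisons are affected by an amount the documents cannot supply. The illustrated shifts of 0.2 to 2.4 points in success and up to 0.87 points either way in mortality hold only under the assumed inputs. The primary MITT non-inferiority conclusion does not depend on this. It should be corrected, but it is not a threat to the main result.

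**What to change.** In the interruption item of SAP 3.2.8 and 3.2.9, replace *test drug* with the SAP's both-arm term: *investigational drug (IMI-XNW4107 or IMI/REL)*. Add a sentence stating that the criterion is applied identically to both arms before unblinding. The same edit could clarify how the parenthetical count is to be read.

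The cost is a wording change in two bullets before the populations are fixed. If the item has already been programmed literally, a few IMI/REL subjects may leave CE and ME; if it was programmed for both arms, nobody moves. If the SAP is already final, its section 1 provides the route: document the change in the clinical study report, including how the criterion was actually applied.
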